1.10 Circulating Tumor Cell Evaluation in CRPC

When combining therapies, and therefore potentially introducing additive toxicity, utilization of PD biomarkers will enrich our ability to define the population most likely to benefit from such a combination while also ensuring on-target efficacy. As will be done in this trial of hormonal therapies, interrogation of the endocrine system may define PD markers of target inhibition. However, procurement of bio-specimens representative of a patient's disease at the time of disease progression is a key component to personalizing cancer therapy.

Metastatic prostate cancer is particularly challenging as patients routinely metastasize to the bones, a secondary site that is painful to biopsy and unfortunately low relative yield⁴³. A potential source of metastatic prostate cancer specimens is cancer cells in the peripheral blood circulation (circulating tumor cells, CTCs). This trial will explore a CTC interrogation platform that will examine intracellular AR expression. While multiple technologies exist for the enumeration of CTCs, very few allow interrogation of cancer biology critical for utilizing CTCs as a therapy specific predictive biomarker. Furthermore, little attention has been paid to the analytic development of these assays, which is critical in the development of any CTC isolation platform. This trial will be essential in clinical validation of a new multi-step technique (see section 12.1 below) that allows for the evaluation of therapeutic target expression within CTCs in real time. State of the art flow cytometry with embedded digital microscopy and recently developed fluorescently conjugated primary antibodies allows the interrogation of intracellular AR and GR simultaneously. The novel multi-marker interrogation methodologies will allow for preliminary studies validating AR/GR status within CTCs as a predictive therapeutic biomarker for targeted therapies. This trial will

analyze the reproducibility and variability of these measures.

2.0 OBJECTIVES

2.1 Primary Objective

- Phase I: To establish the safe and pharmacologically active doses of mifepristone and enzalutamide to use in combination.
- Phase II: To determine if mifepristone in combination with enzalutamide prolongs time to PSA progression compared to enzalutamide alone in patients with metastatic castration resistant prostate cancer

2.2 Secondary Objectives

- To evaluate the effect of mifepristone on endocrine biomarkers such as serum cortisol and thyrotropin.
- To determine the effect of mifepristone on enzalutamide clearance and steady state enzalutamide exposure.
- To determine if mifepristone affects PSA response rate when added to enzalutamide.
- To determine if mifepristone when added to mifepristone prolongs radiographic and clinical progression free survival according to standard working group criteria⁴⁴.
- To explore the role of GR and AR protein expression within circulating tumor cells as a pharmacodynamic biomarker for mifepristone and enzalutamide in CRPC.
- To explore the expression of GR and down-stream AR/GR targets in metastatic tumor specimen prior to combination drug administration and at clinical progression.

3.0 PATIENT SELECTION

3.1 Eligibility Criteria

1. Histologically or cytologically confirmed prostate cancer
2. Evidence of castrate testosterone level <50ng/dL (or surgical castration)
3. For Phase I portion of the study: Evidence of disease progression:
 - 2 or more new lesions on bone scan or
 - Progressive disease on CT/MRI according to RECIST 1.1 criteria⁴⁵ or
 - Rising PSA: PSA evidence for progressive prostate cancer consists of a minimum PSA level of at least 2 ng/ml, which has subsequently risen on at least 2 successive occasions, at least 2 weeks apart.
4. For Phase II portion of the study:

- Subjects must be on enzalutamide for metastatic CRPC and within the first 12 weeks of enzalutamide at 160mg/day
- Record of subject's enzalutamide start date and baseline PSA (within 28 days of starting) before starting enzalutamide available

5. Subjects must have documented clinically stable disease or better during the screening period of the study (see Section 7.1) as defined by all of the following (for Phase II portion of the study):

- PSA \leq 1.25 times the PSA at start of enzalutamide
- Lack of radiographic progression as defined by RECIST 1.1 and Prostate Cancer Working Group Criteria⁴⁴⁻⁴⁶
- Clinically stable as confirmed by treating physician

6. Any prior therapy for castrate disease is acceptable except prior specific CYP17 antagonists (e.g. abiraterone acetate, orteronel) or prior second generation AR antagonists (e.g. enzalutamide or ARN509) which are excluded other than enzalutamide as specified for phase II portion. A minimum washout of 28 days for any other anticancer therapy prior to first dose of study drug is required (only applicable for phase I).

7. Any other radiotherapy or radionuclide require 28-day washout prior to first dose of study drug.

8. Denosumab or zoledronic acid are allowed.

9. ECOG performance status \leq 2 (Appendix A).

10. Patients must have normal hepatic function as defined below:

• Total bilirubin	\leq 1.5 x the upper limit of normal
• AST(SGOT)/ALT(SGPT)	\leq 2.5 X institutional upper limit of normal

11. Ability to understand and the willingness to sign a written informed consent document.

3.2 Exclusion Criteria

1. Therapy with other hormonal therapy, including any dose of megestrol acetate (Megace), finasteride (Proscar), dutasteride (Avodart), or any herbal product known to decrease PSA levels (e.g., saw palmetto and PC-SPES), or any systemic corticosteroid within 2 weeks prior to first dose of study drug.
2. Inability to swallow capsules or known gastrointestinal malabsorption.
3. History of other malignancies, with the exception of: adequately treated non-melanoma skin cancer, adequately treated superficial bladder cancer, stage 1 or 2 solid tumor

malignancies who are without evidence of disease, or other solid tumors curatively treated with no evidence of disease for \geq 5 years from enrollment.

4. Blood pressure that is not controlled despite > 2 oral agents (SBP > 160 and DBP > 90 documented during the screening period with no subsequent blood pressure readings $< 160/100$).
5. History of seizure disorder or active use of anticonvulsants.
6. QTc on EKG > 450 msec
7. Serious intercurrent infections or non-malignant medical illnesses that are uncontrolled.
8. Active psychiatric illness/social situations that would limit compliance with protocol requirements.
9. NYHA class II, NYHA class III, or IV congestive heart failure (any symptomatic heart failure).
10. Concurrent therapy with strong inhibitors or inducers of CYP3A4 or CYP2C8 (See Section 9.12 below for list of strong inhibitor or inducers) due to concerning possible drug-drug interactions

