7.1 Pre-treatment Screening Evaluation

Eligible patients who have signed informed consent and have had eligibility confirmed will be seen in the outpatient clinic within two weeks of starting the study. They will undergo a history and physical examination, have ECOG performance status, concomitant medications, and baseline toxicity documented at this visit. In addition, to confirm eligibility, the patient will have standard of care screening labs drawn within four weeks of initiating therapy. These include: CBC (white blood cell count, hemoglobin, platelet count, white blood cell differential) and serum chemistries (sodium, potassium, chloride, bicarbonate, blood urea nitrogen, creatinine, glucose, calcium, alanine aminotransferase, aspartate aminotransferase, total bilirubin, total protein, alkaline phosphatase, and albumin), LDH, serum testosterone and

PSA. A whole blood sample for circulating tumor cell correlative study will be performed during the screening period and processed as described in Section 12.1. An optional pre-study tumor biopsy will be obtained during screening period (see section 12.2). Subjects will have an EKG to insure normal QTc prior to enrolling.

Disease burden evaluation with a nuclear medicine bone scan (or Fluoride PET), abdominal/pelvis imaging (CT or MRI), and CT chest (when clinically indicated) must be obtained within 30 days of study entry. Study entry date is defined as day of first on-study treatment as detailed in Section 5.1-5.3.

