9.4 Treatment Management of Hypertension

Hypertension may develop while on mifepristone due to excess mineralocorticoid activity due to treatment dependent increase in ACTH. Because of this, hypertension occurring secondary to mifepristone may be most effectively prevented through the concurrent administration of eplerenone which is capable of inhibiting mineralocorticoid induced hypertension. The following table provides a recommended algorithm for treatment-emergent hypertension management. Decisions to hold or decrease the dose of study treatment must be based on blood pressure (BP) readings confirmed with a second measurement at least 5 minutes after the first measurement.

BP Measurements – Systolic/Diastolic	Treatment/Dose Modification
> 140 mm Hg (systolic) and <160 mm Hg OR > 90 mm Hg (diastolic) and < 105 mm Hg OR	
• Add new or additional antihypertensive medications or increase dose of existing medications.• Maintain dose of study treatment.
≥ 160 mm Hg (systolic) OR ≥ 105 mm Hg (diastolic)	
• Hold mifepristone.• Add new or additional anti-hypertensive medications or increase dose of existing medications.• Monitor subject closely for hypotension (if on anti-hypertensive medications) until study treatment is restarted.• Resume treatment at same dose level when BP falls to < 140/90 mm Hg.

If toxicity occurs, hold study treatment, adjust or add medications to mitigate the toxicity. When resolved to \leq Grade 1, resume study treatment with first dose level reduction.

If toxicity recurs at the first dose level reduction, hold study treatment, adjust or add medications to mitigate the toxicity. When resolved to \leq Grade 1, resume study treatment with the second dose level reduction.

[Rest of Page Intentionally Left Blank for Formatting Purposes]

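### Exclusion 4 joins its systolic and diastolic limits with 'and', so a patient on more than two agents with only one value high is not excluded, even at a pressure that fails the criterion's own clearing limit

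*Combined protocol and SAP*

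**What the plan says.** Item 4 of Section 3.2 (Exclusion Criteria) reads: "Blood pressure that is not controlled despite > 2 oral agents (SBP > 160 and DBP > 90 documented during the screening period". It goes on to lift the exclusion if a later reading is below 160/100. Three things must therefore hold together before the criterion applies: more than two oral agents, systolic above 160, and diastolic above 90.

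Section 9.4 (Treatment Management of Hypertension) gives the reason to care: "Hypertension may develop while on mifepristone due to excess mineralocorticoid activity". Its table holds mifepristone at "≥ 160 mm Hg (systolic) OR ≥ 105 mm Hg (diastolic"), with no reference to the number of agents. In the band below that (140 to 160 systolic, or 90 to 105 diastolic) it adds or increases antihypertensives and says "Maintain dose of study treatment". After a hold, treatment resumes below 140/90. A decision to hold or reduce rests on a reading "confirmed with a second measurement at least 5 minutes after the first measurement". The section describes its table as one that "provides a recommended algorithm for treatment-emergent hypertension management".

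Item 7 of Section 3.2 separately excludes "Serious intercurrent infections or non-malignant medical illnesses that are uncontrolled", without a number. Under Section 7.1, patients "will be seen in the outpatient clinic within two weeks of starting the study". The Study Calendar (Section 8.0) schedules vital signs, including blood pressure, at screening and on Days 1, 15 and 29, with no threshold attached.

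**The concern.** Item 4 is meant to keep out patients whose pressure stays high on three or more drugs. With 'and', it catches them only when both values are high at once. A patient with systolic pressure alone, or diastolic pressure alone, well over the limit is just as uncontrolled but does not meet the definition.

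The sentence is also at odds with itself. Its clearing test requires both values to be low, so the natural opposite is that either value being high should count. Instead, a reading can fail the clearing test without ever having triggered the criterion. The diastolic limit moves from 90 in the trigger to 100 in the clearing test, with no reason given.

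At stake is the safety of a small group, and consistent handling across sites. Read literally, such a patient could enter and start a drug that may raise blood pressure, at a level where Section 9.4 would hold it in someone already taking it. Two sites could reasonably decide differently on the same reading.

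**Working it through.** There is no figure in the plan to reproduce. The check sets two rules side by side.

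Inputs:
- Trigger (3.2, item 4): agents >2 and SBP >160 and DBP >90.
- Clearing limit (3.2, item 4): a later reading <160/100, taken as both SBP <160 and DBP <100.
- Hold level (9.4): SBP ≥160 or DBP ≥105.
- Proposed trigger: agents >2 and (SBP ≥160 or DBP ≥100), with the clearing limit unchanged.

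Illustrative readings, all on three agents:

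| Reading | Triggers item 4 now? | Meets the clearing limit? | At the 9.4 hold level? | Triggers as reworded? |
|---|---|---|---|---|
| 175/85 | No (85 is not >90) | No | Yes, 175 − 160 = 15 above | Yes |
| 150/110 | No (150 is not >160) | No | Yes, 110 − 105 = 5 above | Yes |
| 160/110 | No (160 is not >160) | No | Yes | Yes |
| 175/95 | Yes | No | Yes | Yes |
| 150/102 | No | No | No | Yes |
| 155/95 | No | Yes | No | No |

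The first three rows are the gap. The fourth shows the criterion working when both values are high.

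A count over whole-number readings shows that the examples are not isolated. Take SBP 120–200 and DBP 60–120, which gives 81 × 61 = 4,941 combinations, on three agents:
- Below the hold level: SBP 120–159 with DBP 60–104, 40 × 45 = 1,800. At the hold level: 4,941 − 1,800 = 3,141.
- Triggering item 4 now: SBP 161–200 with DBP 91–120, 40 × 30 = 1,200. All of these are at the hold level.
- At the hold level but not triggering: 3,141 − 1,200 = 1,941.
- As reworded: not triggering is SBP 120–159 with DBP 60–99, 40 × 40 = 1,600, so 4,941 − 1,600 = 3,341 trigger. These comprise all 3,141 hold-level combinations plus 200 with SBP <160 and DBP 100–104.

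These are counts of number pairs, not of patients, and say nothing about how common such readings are.

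Two properties of the rewording follow directly. Every reading that triggers now has SBP >160, so it still triggers. The new trigger is also the exact complement of the clearing limit, so no reading can fail one without meeting the other.

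Swapping 'and' for 'or' while keeping 90 would not work. A reading of 150/95 would trigger, and the same 150/95 taken again would clear it. The diastolic limits have to be reconciled at the same time.

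**The case against.** The strongest reply is that item 4 and Section 9.4 serve different purposes. Item 4 screens for resistant hypertension; 9.4 is a recommended algorithm for pressure that rises on treatment. Their thresholds need not match, and the agent count may be deliberate. Judgement also remains available: item 7 can be applied to serious uncontrolled illness, Section 9.1 has patients wait for instruction before taking any dose, and blood pressure is measured at screening and at the early visits. There is usually time to treat a high reading, since the screening visit may be up to two weeks before the start and Phase I adds a 28-day enzalutamide lead-in.

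Most of this stands, and it limits how far the point can go. A reader might infer that no numeric limit stands between any patient and the first mifepristone dose, or that admitting patients on zero to two agents at any pressure is an error. The documents do not support either. Item 4 is itself a numeric entry limit for patients on more than two agents. Restricting it to them is a defensible choice, and the text elsewhere leaves room to refuse or delay. It is true that no limit is attached to the reading on the dosing day, but that is a missing detail left to the investigator, not a contradiction.

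The reply does not reach the 'and'. That defect affects exactly the patients a resistant-hypertension screen is meant to catch, and it shows from item 4's own clearing limit without any appeal to 9.4. The 90 versus 100 mismatch likewise lies within one sentence.

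**Conclusion.** The point holds as a drafting defect in item 4. On more than two agents, a high systolic or a high diastolic value alone does not exclude, although such readings fail the criterion's own clearing limit and can be at the hold level of Section 9.4. The trigger and clearing diastolic limits disagree by 10 mm Hg.

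This rests on reading the 'and' literally and on reading the clearing limit as requiring both values to be low. Section 9.4 serves only as a benchmark for what the protocol regards as too high while on the drug; it is not an entry rule. The readings shown are illustrations. The number of patients affected cannot be estimated from the documents and may be small. The Phase II sample size (84), power (80%) and one-sided alpha (0.10) do not depend on it. It is a minor safety correction, worth making because it is cheap.

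**What to change.** Keep the opening of item 4, including the condition of more than two oral agents, and replace the bracket with: SBP ≥160 or DBP ≥100 during screening, with no subsequent reading that is both <160 systolic and <100 diastolic. Whether to keep the agent count is for the sponsor.

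The cost is one reworded criterion in an amendment, with no new visits required by the protocol. A few patients on more than two agents will need their pressure controlled and re-read before entry. They include some with a diastolic of 100–104, which is below the 9.4 hold level but already fails the present clearing limit.

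A numeric check on the day of the first mifepristone dose is optional and not needed for this correction. If the sponsor adds one, it should say how it relates to the <140/90 level that 9.4 requires before resuming after a hold. It should also say what happens to a Phase II patient whose pressure is still high when the start window closes at week 14. A check applied only to the mifepristone arm after randomization would delay study treatment in that arm alone, while the primary endpoint runs from randomization.

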3.3 Inclusion of Minorities

Men of all races and ethnic groups are eligible for the trial.

4.0 REGISTRATION AND DATA COLLECTION/MANAGEMENT

4.1 Registration Process

Prior to registration, potential patients must have documented ability and willingness to procure standard commercially available enzalutamide (Xtandi®). Prior authorization assistance for commercially available enzalutamide is available through the manufacturer:

<http://www.astellasaccess.com/home/pat/xtandi/>

The University of Chicago Comprehensive Cancer Center maintains a secure, password protected, and regularly backed up commercial clinical trials database called “Velos.” Patients on the trial will be entered into the Velos database centrally at the University of Chicago by the study coordinator. Data will be entered by the study coordinator and stored within the database using the patient-study number as well as a unique identifier generated by Velos.

Study Coordinator:

[name]
University of Chicago, Department of Medicine
Section of Hematology/Oncology

[name]
[contact]
[contact]
[contact]

Eligible patients will be entered on study centrally at the University of Chicago by the Study Coordinator. Forms are available to UC Phase II Personalized Cancer Care Consortium (PCCC) Affiliates on the University of Chicago Cancer Research Center website.

<http://cancer.uchicago.edu/trials/pccc/index.shtml>

Click on the Log in to access

Enter your site specific user name and password

For non-UC Consortium affiliates, forms will be provided by request from the study coordinator.

The following baseline clinical variables will be collected and stored in the database using data entry forms all available in the Velos database (Appendix B):

- Demographics
- Age
- Race
- Performance status
- Primary tumor data
- Diagnosis date
- Baseline staging
- Baseline PSA
- Gleason grade
- Primary tumor treatment
- Systemic therapy administered
- Date of androgen ablation start
- Dates of anti-androgen therapy, and withdrawal
- Dates and types of other systemic therapy
- Dates and types of systemic radiotherapy
- Sites of metastatic disease

Patients can be registered only after the initial IRB approval for the participating site has been forwarded to the Coordinating Center, University of Chicago.

All patients must be registered with the University of Chicago Study Coordinator. The following documents should be completed by the research nurse or data manager and faxed to [contact] or emailed to the study coordinator at:

[contact] a minimum of 48 hours prior to expected study med start date:

- Provider of information
- Treating Physician (NCI investigator number)
- Patient name and hospital ID number

- Patient's zip code of residence
- Date & copy of signed informed consent
- Race, gender, date of birth of patient
- Diagnosis and date of initial diagnosis
- Complete Phase II Consortium Affiliate Clinical Trial Patient Registration Form
- Source documentation for eligibility and pre-study procedures
- Prior authorization and documentation of enzalutamide availability

The research nurse or data manager at the participating site will then call the study coordinator to confirm all selection criteria listed in Section 3.0.

To complete the registration process, the UCMC Coordinator will:

- Assign a patient study number
- Register the patient on the study
- Fax or e-mail the patient study number to the participating site
- Fax or e-mail, within 28 hours of completed registration, the assigned treatment dose (for phase I portion) or treatment arm (for phase II portion)
- Call the research nurse or data manager at the participating site and verbally confirm registration.

4.2 Treatment Allocation and Randomization Processes

For the phase I portion of the study, based on the dosing schema described below, study subjects will be assigned the applicable doses of mifepristone and enzalutamide. The dose level will be included in the registration information provided by the study coordinator as in Section 4.2 above.

For the phase II portion of the study, eligible registered subjects will be randomized to either continue standard dose enzalutamide at 160mg/day orally or to the enzalutamide and mifepristone at the Recommended Phase II Dose (See Section 5.3). Patients will be randomized by the University of Chicago Cancer Clinical Trials Office (CCTO), in cooperation with the Biostatistics Core Facility of the UCCRC. Patients will remain on their allocated treatment arm throughout the duration of study therapy with no crossover while on study. Participating sites will be notified by the coordinator within 48-hours of registered patient's open label, randomized treatment group assignment.

5.0 STUDY DRUG ADMINISTRATION

Treatment will be administered on an outpatient basis continuously. Study drug is commercially available and will be procured by the patient through their pharmacy. A specialty pharmacy may be needed. As noted above (Section 4.1), prior authorization and documentation of enzalutamide availability is necessary prior to registration.

Mifepristone will be provided by Corcept Therapeutics and shipped to the University of Chicago for use on site and distribution to participating institutions upon patient registration and treatment allocation. The mifepristone will be provided as 300mg tablets, 30 tablets/bottle. Appropriate number of bottles will be dispersed by the investigator to the patient depending on the treatment dose allocation. Each bottle provided to the subjects will be labeled with the protocol number, dosing and storage instructions, and expiration

date. The contents of the label will be in accordance with applicable regulatory requirements.

The mifepristone may be requested by the Principal Investigator (or their authorized designees) at the University of Chicago. Corcept will only ship the agent directly to the University of Chicago. Other sites who require study agent should submit a completed Clinical Drug Request Forms to the University of Chicago Investigational Drug Service by [contact]. Orders received on Fridays will not be shipped until the following business day.

For questions about drug orders, transfers, returns, or accountability call [contact] Monday through Friday between 8:00 am and 4:30 pm (CST) or email [contact] anytime.

Agent Inventory Records – The investigator, or a responsible party designated by the investigator, must maintain a careful record of the inventory and disposition of all

As noted in Figure 2 Trial Schema, this clinical trial consists of two parts:

- Phase I portion, in which the doses of enzalutamide and mifepristone will be adjusted based on safety and pharmacokinetics to reach the Recommended Phase II Dose (RP2D)
- Phase II randomized study of mifepristone and enzalutamide at RP2D versus enzalutamide alone

5.1 Study Drug administration for each portion is as follows.

